Appendix 2 Schedule of Assessments

| PK RUN-IN COHORT | | | | | | | | | | | | | | | | |
|---|------------------|-----------|------------------------------|---|----------------|----|----|----------------|----------------|----------------|----------------|----------------|--|--|---------------------|---|
| | Screening | | Treatment Period | | | | | | | | | | From Week 25 to Study Completion | Study Completion or Early Termination ^a | Safety F/U Visit | |
| | Week | — | — | 1 | 2 | 3 | 4 | 5 | 9 | 13 | 17 | 21 | 25 | | | |
| | Day ^b | -28 to -1 | -7 to -1 | 1 | 8 | 15 | 22 | 29 | 57 | 85 | 113 | 141 | 169 | | | |
| Informed consent ^c | x | | | | | | | | | | | | | | | |
| Inclusion/exclusion criteria | x | | | | | | | | | | | | | | | |
| Demographics and medical history ^d | x | | | | | | | | | | | | | | | |
| Physical examination including height and weight ^e | x | | x ^f | | x ^f | | | x ^f | x ^f | x ^f | x ^f | x ^f | x ^f | Q12W ^f | x ^f | x |
| Vital signs ^g | x | | x | x | | x | x | x | x | x | x | x | x | Q12W | x | x |
| Concomitant medications ^h | | | x | | x | | x | x | x | x | x | x | x | Q12W | x | x |
| Adverse events ⁱ | | | Ongoing | | | | | | | | | | | | | |
| 12-lead ECG ^j | x | | | | | | | x ^k | | | | | x | x ^l | x | |
| Hematology ^m | | x | x | x | x | | | x | x | x | x | x | x | Q12W | x | x |
| Blood chemistry ⁿ | | x | x | x | x | | | x | x | x | x | x | x | Q12W | x | x |
| Pregnancy test ^o | x | x | x | x | x | | | x | x | x | x | x | x | Q12W | x | x |
| Emicizumab administration ^p | | | x | | | | | x | x | x | x | x | x | Q4W | | |
| PK, PD, and ADA | See protocol | | | | | | | | | | | | | | | |
| Bleed /medication questionnaire ^q | | | Weekly and on days of bleeds | | | | | | | | | | | x | x | |

Appendix 2 Schedule of Assessments (cont.)

| PK RUN-IN COHORT | | | | | | | | | | | | | | | | |
|---|-----------|----------|--|---|----|----|----|----|----|-----|-----|-----|--|--|---------------------|--|
| | Screening | | Treatment Period | | | | | | | | | | From Week 25 to Study Completion | Study Completion or Early Termination ^a | Safety F/U Visit | |
| | Week | — | — | 1 | 2 | 3 | 4 | 5 | 9 | 13 | 17 | 21 | 25 | | | |
| Day ^b | -28 to -1 | -7 to -1 | 1 | 8 | 15 | 22 | 29 | 57 | 85 | 113 | 141 | 169 | | | | |
| Bleed/medication review ^r | | | x | | | | x | x | x | x | x | x | Q4W | x | x | |
| Following treatment with bypassing agents ^s | | | Monitoring for thromboembolic events and thrombotic microangiopathy. ^s | | | | | | | | | | | | | |

ADA = anti-drug antibody; eCRF = electronic Case Report Form; EQ-5D-5L = European Quality of Life-5 Dimensions-5 Levels; F/U = follow-up; HRQoL = health-related quality of life; PD = pharmacodynamic; PK = pharmacokinetic; PRO = patient-reported outcome; Q4W = every 4 weeks; Q12W = every 12 weeks.

- ^a Study completion visit when either the patient completed 24 weeks' study duration and transferred to an emicizumab extension study OR patient has completed the 24-week safety follow-up visit after emicizumab discontinuation OR patient is lost to follow-up. If study completion occurs after 24 weeks in the study, the completion assessments displayed in the schedule of assessments are similar with the Week 25 visit.
- ^b In order to characterize pharmacokinetics, it is mandatory assessments be performed on the exact visit day until Week 25; no deviation from visit day is acceptable *until Week 25, deviations of ± 2 days are acceptable thereafter.*
- ^c Obtain written informed consent (or patient written assent and parent written informed consent if patient is an adolescent) before performing any study related procedures. *If patient fulfils the inclusion criteria, the patient should be enrolled in the study on the same day when the first dose of emicizumab is administered (Day 1).*
- ^d Collected from patient's medical record and documented in the eCRF.
- ^e Height assessment at Day 1 only for adults and weight assessments Q4W for all patients.
- ^f Height assessments for adolescents at Day 1 and ideally at all drug administration and PK sampling visits when the patients will be at the investigational site but at least every 12 weeks (repeated assessments).
- ^g Body temperature (oral or tympanic), blood pressure, pulse rate, respiratory rate.
- ^h Concomitant medication (e.g., extra pain medication to treat bleeds) will be recorded at the time of the visits, excluding treatments for bleeds, which will be collected in the bleeding questionnaire.

Appendix 2 Schedule of Assessments (cont.)

-
- ⁱ Adverse events are collected on an ongoing basis throughout the study. Injection-site reactions will be collected on a separate form from the adverse event form. After informed consent has been obtained, but prior to initiation of study drug, only serious adverse events caused by a protocol-mandated intervention should be reported.
- ^j If screening ECG is abnormal, repeat at Week 1. ECGs will also be performed: once during Weeks 4–8 after starting emicizumab or dose escalation (up-titration); once 24 weeks after starting emicizumab or dose escalation (up-titration); and at study completion/early termination.
- ^k Once during Weeks 4–8 after starting emicizumab.
- ^l For any dose increase (i.e., 3 mg/kg QW), an ECG should be obtained after 4 weeks of starting the new dose at the next scheduled clinic visit.
- ^m Predose (hemoglobin, hematocrit, platelet count, RBC count, WBC count, absolute differential count [neutrophils, eosinophils, lymphocytes, monocytes, basophils, other cells], mean corpuscular volume, mean corpuscular hemoglobin, mean corpuscular hemoglobin concentration, and RBC distribution width), performed locally. Laboratory assessments completed at the screening visit do not have to be repeated at Week 1 if the period between Screening and Week 1 is 5 days or less and there has been no change in health status as assessed by the investigator.
- ⁿ Predose (sodium, potassium, glucose, blood urea nitrogen, creatinine, calcium, phosphorus, magnesium, total and direct bilirubin, albumin, alanine aminotransferase, aspartate aminotransferase, and alkaline phosphatase), performed locally. Laboratory assessments completed at the screening visit do not have to be repeated at Week 1 if the period between Screening and Week 1 is 5 days or less and there has been no change in health status as assessed by the investigator.
- ^o Female patients with childbearing potential will be required to have a negative serum pregnancy test result at Screening and up to 7 days prior to enrollment (Day –7 to Day –1). If applicable, during the study, urine pregnancy tests will be performed at the scheduled visits.
- ^p 6 mg/kg Q4W emicizumab.
- ^q Bleed information (start date and time, reason, type, location, and associated symptoms of each bleed) and medication for bleeds (breakthrough bleeds) should be reported by the patient via an electronic handheld device when a bleed occurs or at least on a weekly basis (retrospective reporting for last 7 days). *If the patient discontinues study treatment, bleed and bleed medication data should be provided by the patient until the safety follow-up visit (24 weeks after last study drug administration).*
- ^r Investigator review of bleed information.
- ^s *Following bypassing agent treatment, patients should provide a sample for local laboratory monitoring of thromboembolic events and thrombotic microangiopathy for platelet count, serum creatinine, LDH, and schistocytes within 24–48 hours of initial bypassing agent use. A plasma sample should also be provided for local (one aliquot) and central (a second aliquot) laboratory monitoring of fibrinogen, prothrombin fragment 1+2, and D-dimer. If prothrombin fragment 1+2 test cannot be done at the site, the sample should be sent to the local reference laboratory, if available. For patients who require multiple doses of bypassing agents, laboratory monitoring should be performed every 24–48 hours thereafter until 24–48 hours following the last dose of bypassing agents administered to treat a given bleed. If applicable, laboratory results should be recorded on the unscheduled visit eCRFs.*

Appendix 2 Schedule of Assessments (cont.)

| Expansion Cohort | | | | | | | | | | | | | | | |
|---|------------------|-----------|------------------|---|----------------|----|----------------|----------------|----------------|----------------|----------------|----------------|----------------------------------|--|------------------------|
| | Screening | | Treatment Period | | | | | | | | | | From Week 25 to Study Completion | Study Completion or Early Termination ^a | Safety Follow-Up Visit |
| | | | | | | | | | | | | | | | |
| | Day ^b | -28 to -1 | -7 to -1 | 1 | 8 | 15 | 22 | 29 | 57 | 85 | 113 | 141 | 169 | | |
| Informed consent ^c | x | | | | | | | | | | | | | | |
| Inclusion/exclusion criteria | x | | | | | | | | | | | | | | |
| Demographics and medical history ^d | x | | | | | | | | | | | | | | |
| Physical examination including height and weight ^e | x | | x ^f | | x ^f | | x ^f | x ^f | x ^f | x ^f | x ^f | x ^f | Q12W ^f | x ^f | x |
| Vital signs ^g | x | | x | x | | x | x | x | x | x | x | x | Q12W | x | x |
| Concomitant medications ^h | | | x | | x | | x | x | x | x | x | x | Q12W | x | x |
| Adverse events ⁱ | | | Ongoing | | | | | | | | | | | | |
| 12-lead ECG ^j | x | | | | | | x ^k | | | | | x | x ^l | x | |
| Hematology ^m | | x | x | x | x | x | x | x | x | x | x | x | Q12W | x | x |
| Blood chemistry ⁿ | | x | x | x | x | x | x | x | x | x | x | x | Q12W | x | x |

Appendix 2 Schedule of Assessments (cont.)

| Expansion Cohort | | | | | | | | | | | | | | | | | |
|---|------------------|-----------|--|---|---|----|----|----|----|----|----------------|-----|----------------------------------|--|------------------------|---|--|
| | Screening | | Treatment Period | | | | | | | | | | From Week 25 to Study Completion | Study Completion or Early Termination ^a | Safety Follow-Up Visit | | |
| | Week | — | — | 1 | 2 | 3 | 4 | 5 | 9 | 13 | 17 | 21 | 25 | | | | |
| | Day ^b | -28 to -1 | -7 to -1 | 1 | 8 | 15 | 22 | 29 | 57 | 85 | 113 | 141 | 169 | | | | |
| Pregnancy test ^o | x | x | x | x | x | x | x | x | x | x | x | x | x | Q12W | x | x | |
| PRO (HRQoL) ^p | | | x | | | | | | | x | | | x | Q12W | x | | |
| Days missed from school/work^q | | | x | | | | | | | x | | | x | Q12W | x | | |
| PRO (Preference) | | | | | | | | | | | x ^r | | | | | | |
| Health status (EQ-5D-5L) ^s | | | x | | | | | | | x | | | x | Q12W | x | | |
| Emicizumab administration ^t | | | x | x | x | x | x | x | x | x | x | x | x | Q4W | | | |
| PK, PD, ADA | See protocol | | | | | | | | | | | | | | | | |
| Bleed/medication questionnaire ^u | | | Weekly and on days of bleed | | | | | | | | | | | x | x | | |
| Bleed/medication review ^v | | | x | | | | | x | x | x | x | x | x | Q4W | x | x | |
| Following treatments with bypassing agents^w | | | Monitoring for thromboembolic events and thrombotic microangiopathy^w | | | | | | | | | | | | | | |

Appendix 2 Schedule of Assessments (cont.)

ADA = anti-drug antibody; eCRF = electronic Case Report Form; EQ-5D-5L = European Quality of Life-5 Dimensions-5 Levels; ET = early termination; F/U = follow-up; FIX = factor IX; FVIII = factor VIII; FX = factor X; FXIII = factor XIII; HRQoL = health-related quality of life; PD = pharmacodynamic; PK = pharmacokinetic; PRO = patient-reported outcome; Q4W = every 4 weeks; Q12W = every 12 weeks.

- ^a Study completion visit when either the patient completed 24 weeks' study duration and transferred to an emicizumab extension study OR patient has completed the 24-week safety follow-up visit after emicizumab discontinuation OR patient is lost to follow-up. If study completion occurs after 24 weeks in the study, the completion assessments displayed in the schedule of assessments are similar with the Week 25 visit.
- ^b Assessments can deviate from planned schedule by ± 2 days.
- ^c Obtain written informed consent (or patient written assent and *legal representative* written informed consent if patient is an adolescent) before performing any study related procedures. *If patient fulfils the inclusion criteria, the patient should be enrolled in the study on the same day when the first dose of emicizumab is administered (Day 1).*
- ^d Collected from patient's medical record and documented in the eCRF.
- ^e Height assessment at Day 1 only for adults and weight assessments Q4W for all patients.
- ^f Height assessments for adolescents at Day 1 and ideally at all drug administration and PK sampling visits that the patients will be at the investigational site, but at least every 12 weeks (repeated assessments).
- ^g Body temperature (oral or tympanic), blood pressure, pulse rate, respiratory rate.
- ^h Concomitant medication (e.g., extra pain medication to treat bleeds) will be recorded at the time of the visits, excluding treatments for bleeds, which will be collected in the bleeding questionnaire *starting from Day 1. FVIII taken in the week prior to starting emicizumab (week prior to Day 1) will also be collected on the Concomitant Medication eCRF page for patients without inhibitors to FVIII who will continue their prior FVIII prophylaxis during the first week of the study.*
- ⁱ Adverse events are collected on an ongoing basis throughout the study. Injection-site reactions will be collected on a separate form from the adverse event form. After informed consent has been obtained, but prior to initiation of study drug, only serious adverse events caused by a protocol-mandated intervention should be reported.
- ^j If screening ECG is abnormal, repeat at Week 1. *ECGs will also be performed: once during Weeks 4–8 after starting emicizumab or dose escalation (up-titration); once 24 weeks after starting emicizumab or dose escalation (up-titration); and at study completion/early termination.*
- ^k *Once during Weeks 4–8 after starting emicizumab.*
- ^l For any dose increase (i.e., 3 mg/kg/wk), an ECG should be obtained after 4 weeks of starting the new dose at the next scheduled clinic visit.
- ^m Predose: (hemoglobin, hematocrit, platelet count, RBC count, WBC count, absolute differential count [neutrophils, eosinophils, lymphocytes, monocytes, basophils, other cells], mean corpuscular volume, mean corpuscular hemoglobin, mean corpuscular hemoglobin concentration, and RBC distribution width), performed locally. Laboratory assessments completed at the Screening visit do not have to be repeated at Week 1 if the period between Screening and Week 1 is 5 days or less and there has been no change in health status as assessed by the investigator.

Appendix 2 Schedule of Assessments (cont.)

- ⁿ Predose (e.g., sodium, potassium, glucose, blood urea nitrogen, creatinine, calcium, phosphorus, magnesium, total and direct bilirubin, albumin, alanine aminotransferase, aspartate aminotransferase, and alkaline phosphatase), performed locally. Laboratory assessments completed at the Screening visit do not have to be repeated at Week 1, if the period between Screening and Week 1 is 5 days or less and there has been no change in health status as assessed by the investigator.
- ^o Female patients with childbearing potential will be required to have a negative serum pregnancy test result at Screening and up to 7 days prior to enrollment (Day – 7 to Day – 1). If applicable, during the study, urine pregnancy tests will be performed at the scheduled visits.
- ^p Day 1 assessment predose (= baseline), followed by assessments at Week 13 predose and Week 25 predose by Haem-A-QoL (age > 18 years) and Haemo-QoL-Short Form (ages 12–17 years).
- ^q *Day 1 assessment predose (=baseline), followed by assessments at Week 13 predose and Week 25 predose.*
- ^r Predose.
- ^s Day 1 assessment predose (= baseline), followed by assessments at Week 13 predose and Week 25 predose by EQ-5D-5L questionnaire.
- ^t 3 mg/kg Q4W emicizumab loading dose, followed by 6 mg/kg Q4W emicizumab maintenance dose.
- ^u Bleed information (start date and time, reason, type, location, and associated symptoms of each bleed) and medication for bleeds (breakthrough bleeds) should be reported by the patient via an electronic, handheld device when a bleed occurs or at least on a weekly basis (retrospective reporting for last 7 days). *If the patient discontinues study treatment, bleed and bleed medication data should be provided by the patient until the safety follow-up visit (24 weeks after last study drug administration).*
- ^v Investigator review of bleed information.
- ^w *Following bypassing agent treatment, patients should provide a sample for local laboratory monitoring of thromboembolic events and thrombotic microangiopathy for platelet count, serum creatinine, LDH, and schistocytes within 24–48 hours of initial bypassing agent use. A plasma sample should also be provided for local (one aliquot) and central (a second aliquot) laboratory monitoring of fibrinogen, prothrombin fragment 1+2, and D-dimer. If prothrombin fragment 1+2 test cannot be done at the site, the sample should be sent to the local reference laboratory, if available. For patients who require multiple doses of bypassing agents, laboratory monitoring should be performed every 24–48 hours thereafter until 24–48 hours following the last dose of bypassing agents administered to treat a given bleed. In the case that such local laboratory tests are performed, laboratory results should be recorded on the unscheduled visit eCRFs.*

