For patients in the PK run-in cohort, all drug administrations in Weeks 1–25 will be conducted at the investigational site by an HCP. Patients who remain in the study after Week 25 will have the option to self-administer emicizumab at home if patient's ability to self-administer the study drug is documented in the source data, except on days when PK assessment is planned (see [Appendix 2](#)). On these days, emicizumab should be administered at the investigational site after the PK sample has been drawn.

Patients in the expansion cohort will also need to come to the site at all times of drug administration in Weeks 1–25 because predose PK and PD samples have to be drawn. Therefore, all SC injections will be performed at the site until Week 25 (unless mobile nursing [MN] is implemented; see [Section 4.5](#)). However, unassisted self-administration of the drug at the investigational site will be supported for patients in the expansion cohort, and patients remaining in the study after Week 25 might have the option to self-administer emicizumab at home. On days when PK samples are to be collected (see [Appendix 2](#)), emicizumab should be administered at the investigational site after the PK sample has been drawn.

Patients/caregivers will be required to complete in-person, instructional training on how to administer emicizumab as an SC injection. Patients/caregivers will be taught to perform the injections utilizing the Instructions for Use document. They will observe at least one SC injection performed by an HCP and will need to successfully administer at least one SC injection under an HCP's watch prior to starting unassisted self-administration.

Details on the devices to be used for study medication withdrawal from vial and SC injection are provided in the Pharmacy Manual.

Any dose modification will be determined from emicizumab data entered into the electronic, handheld device. Cases of overdose, medication error, drug abuse, or drug misuse, along with any associated adverse events, should be reported as described in Section 5.3.5.12.

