- Spontaneous bleeds: Bleeds should be classified as spontaneous if a patient records a bleed when there is no known contributing factor such as definite trauma, antecedent “strenuous” activity or “overuse.” The determination of what constitutes “strenuous” or “overuse” will be at the discretion of the patient. For example, light jogging may be considered “non-strenuous” while sprinting may be considered “strenuous,” lifting of weights for a short period of time may be considered “moderate use” while repetitive weightlifting may be considered “overuse.”
- Traumatic bleeds: Bleeds should be classified as traumatic if a patient records a bleed when there is a known or believed reason for the bleed. For example, if a patient were to exercise “strenuously” and then have a bleed in the absence of any obvious injury, the bleed would be recorded as a traumatic bleed because, although no injury occurred, there was antecedent “strenuous” activity. Bleeds subsequent to injuries would certainly be classified as traumatic.
- Bleeds related to procedure/surgery: such as hematomas resulting from any surgeries or invasive procedures (e.g., tooth extractions, venipuncture, or SC drug administrations) or invasive diagnostic procedures (e.g., lumbar puncture, arterial blood gas determination, or any endoscopy with biopsy, etc.) would not be counted as bleeds. Bleeds related to procedure/surgery are not associated with any trauma except procedure/surgery-induced trauma.

Patients (or their legally authorized representative) will complete a bleed/medication questionnaire weekly and whenever a bleed occurs via an electronic, handheld device. For each bleeding episode, they will provide information on the above topics as well as on the medication used to treat the bleed. Hemophilia medications that were taken will also be collected through the bleed/medication questionnaire. If the electronic, handheld device is not available, a paper questionnaire might be used. Investigators will review the bleed and bleed medication data as per the schedule of assessments (see [Appendix 1](#)) and have the option to correct or complete these in agreement with the patient via a Data Request Form process or via a Web-based portal, once implemented. The Sponsor will have view-access only but will do a review of the bleed and bleed medication data as per the Medical Data Review Plan.

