2.2 COLLECTION OF PATIENT-REPORTED DATA

2.2.1 Collection of Bleed and Medication Data

Bleed and medication data are collected through a bleed and medication questionnaire (BMQ), which was developed by the Sponsor given that no standard questionnaire for collection of this data was available. The BMQ was developed as a patient-reported measure of bleeding episodes (including cause, type, location, and symptoms of bleeds) and hemophilia-related medication use. This questionnaire was initially used in the non-interventional study (NIS; BH29768), patients with inhibitors study (BH29884), and later in the studies for pediatric patients (Study BH29992) and the non-inhibitor patients (Study BH30071).

To capture bleed data, emicizumab use, and other hemophilia medication use during study treatment, patients will complete the BMQ on a handheld device that will be provided to them during the Week 1 visit at the study site. This device will remain with the patient for the duration of the study to enter bleed and medication data weekly at a minimum. In case a patient did not experience any bleeds or administer any treatments for a week, the patient is asked to log into the device and fill in the questionnaire to confirm this. These weekly entries, in addition to the bleeds and medication entries can also be used to assess compliance. Of note, the patient is able to enter bleeds and medications for the past 8 days, including the day the entries are made. This retrospective data entry window was considered acceptable in terms of recall bias and was added in order to optimize the completeness of data collection.

Patients who withdraw from emicizumab treatment will continue to record bleeds and hemophilia medication administration until they complete the safety follow-up visit.

The patient is able to edit and delete bleeds and medications for 24 hours after they are entered. Furthermore, the investigator and patient are instructed to review the data together at every clinic visit. If the patient has been unable to enter data for any reason, the investigator is able to do so using a data clarification request (Data Change Request [DCR]; not subject to the previous 8-day data entry window). Note, the symptoms of joint and muscle bleeds are not collected in this case because the patient may not be

able to reliably remember them. In addition, the investigator is able to request a change be made to the vendor's database by submitting a DCR.

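### Investigator bleed review is scheduled at Week 1 and next at Week 5, so a diary entry missed on about Days 1–21 may be recovered only without the symptoms that the joint-bleed endpoints require

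*SAP*

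**What the plan says.** **Review frequency.** SAP 2.2.1 states that "the investigator and patient are instructed to review the data together at every clinic visit". Protocol 4.5.8 states that "Investigators will review the bleed and bleed medication data as per the schedule of assessments". In SAP Appendix 2 (both cohorts) and protocol Appendix 1 (run-in cohort), the bleed/medication review row is marked at Week 1 and next at Week 5, with nothing at Weeks 2, 3 or 4.

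**Attendance.** Protocol 4.3.2.1 says: "Patients in the expansion cohort will also need to come to the site at all times of drug administration in Weeks 1–25", unless mobile nursing is implemented. The expansion cohort is dosed on Days 8, 15 and 22. Run-in patients give PK samples on Days 8, 11, 15, 18 and 22 (protocol Appendix 2).

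**Entry rules.** The diary device is handed over at the Week 1 visit. Footnotes q and u of the schedule have patients report bleeds "via an electronic, handheld device when a bleed occurs or at least on a weekly basis (retrospective reporting for last 7 days"). SAP 2.2.1 lets the patient enter the past 8 days, including the day of entry. After that the investigator can add a bleed by data change request with no time limit, but "the symptoms of joint and muscle bleeds are not collected in this case".

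**Endpoints.** SAP 2.3.2.4 counts a treated joint bleed only if at least one listed symptom is reported, and protocol 4.5.8 has the same requirement. SAP 2.3.2.5 selects target joint bleeds from treated joint bleeds. The definitions of treated bleeds and all bleeds (SAP 2.3.2.1 and 2.3.2.2) do not use symptoms.

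**The concern.** The two documents give different review frequencies, and the difference falls in the first month, when visits are most frequent. The Week 1 review has no diary data to look at, because the device is issued at that visit. The first informative scheduled review is therefore Day 29, by which time the patient can no longer enter most of the preceding four weeks.

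Two endpoints are at stake. A real joint bleed that the patient failed to enter, and that surfaces at Day 29, goes in by the route that records no symptoms. The SAP has no rule for such a bleed, and the literal definition excludes it. Timing also weakens: SAP 4.9 allows bleed and treatment times to be left blank in site entry, while the 72-hour rule relies on them.

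The period counts. The efficacy period starts at the first dose (SAP 2.3.1), and protocol 3.1.2 singles out the time before steady state as one when breakthrough bleeds may need treatment.

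**Working it through.** No sample size, power or rate figure in the plan bears on this point. The check is a reading of the schedule followed by a count of days.

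**Step 1: where the review marks fall.** Both run-in rows (SAP Appendix 2, protocol Appendix 1) have three blank cells between the Week 1 and Week 5 marks. The SAP expansion row, as extracted, has a surplus column. Aligned on the Week 13 and Week 25 quality-of-life marks, its second review mark is Week 5, and six marks cover Weeks 5, 9, 13, 17, 21 and 25. The protocol expansion row also has a surplus column, with seven marks where six are expected. Week 5 is the natural reading, but the extracted text cannot exclude a Week 4 mark.

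**Step 2: which days are closed at the first informative review.** A bleed on day d can still be entered by the patient at a review on day r if r − d ≤ 7 (8 days including day r). Day 1 here means after the visit.
- Review on Day 29: open from Day 29 − 7 = Day 22. Closed: Days 1–21, that is 21/28 = 75%. Days 22–28 remain open.
- If the entry window were 7 days including the entry day: closed Days 1–22, that is 22/28 = 78.6%.
- Week 5 visit moved by ±2 days (8-day window): Day 27 − 7 = 20, so closed to Day 19; Day 31 − 7 = 24, so closed to Day 23.
- If a Week 4 review (Day 22) existed: Day 22 − 7 = 15, so closed Days 1–14.

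**Step 3: review at every attended visit.** Reviews on Days 8, 15, 22 and 29 give windows of Days 1–8, 8–15, 15–22 and 22–29, so no day is closed on nominal visit days. The expansion cohort allows ±2 days, and two unfavourable patterns show what remains:
- Reviews on Days 10, 13, 24 and 27, then Day 57: closed Days 1, 2, 14, 15, 16 and 28 (6 days).
- Reviews on Days 6, 17, 20 and 31: closed Days 7, 8, 9, 21, 22 and 23 (6 days).

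**Step 4: the first month against the rest.** The first four weeks are 28/168 = 16.7% of a 24-week period. Each later 4-week interval has the same feature. For Days 30–57, the Day 57 review reaches back to Day 50, so Days 30–49 (20 days) are closed. Over 24 weeks that is 21 + 5 × 20 = 121 closed days. Adding reviews at Weeks 2–4 removes 21 of them (21/121 = 17%), leaving 100. In those later intervals expansion patients have no intermediate clinic visit to use.

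**Step 5: what happens to a bleed added late.** In treated bleeds and all bleeds it counts, because no symptom is needed and the data change request has no time limit (treated bleeds also need a recorded treatment). In treated joint bleeds it fails the symptom condition as written. In target joint bleeds it fails because it is not a treated joint bleed.

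**The case against.** The strongest reply is that SAP 2.2.1 is the specific text on bleed collection and already requires review at every clinic visit. If sites follow it, no first-month day is lost on nominal visit days. That stands: the harm is conditional on the schedule governing, and the documents do not settle which text does. But protocol 4.5.8 points sites to the schedule, so the conflict needs resolving.

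There are also safeguards. Patients must log in weekly even to confirm that nothing happened. Entries are transmitted in real time and can be viewed on a portal (protocol 7.3). The sponsor's data manager and Medical Monitor check entries, at no stated frequency. Bypassing-agent use triggers laboratory tests within 24–48 hours (protocol 4.5.5). These may reveal some gaps before Day 29. They are incomplete, because protocol 4.4 generally has medication for bleeds reported only through the device, so a missed bleed may leave little on the eCRF to reconcile against.

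A reader might infer more than the documents support:
- **That all bleed counts are biased downward.** A late-added bleed still enters treated bleeds (with its treatment recorded) and all bleeds. For those, the issue is recall and timing error of unknown size.
- **That 75% of bleeds are affected.** The figure is a share of calendar days. A bleed is affected only if both the as-it-happens entry and the weekly entry fail, and no failure rate is given.
- **That the first month is uniquely exposed.** Step 4 shows that it is not. It differs in having visits at which the gap could be closed.

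**Conclusion.** The inconsistency is real and worth correcting. If the schedule governs, a bleed on about Days 1–21 that the patient did not enter in time can be recovered only without joint or muscle symptoms. Read literally, it then cannot count as a treated joint bleed or a target joint bleed. Those two endpoints may be under-counted. The treated-bleed and all-bleed rates are exposed only to some recall and timing error.

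The size that can be stated is 21 of 28 days, in a month that is 16.7% of a 24-week period. The number of affected bleeds is unknown. The conclusion assumes the 8-day window, nominal visit days, a Week 5 (not Week 4) second review in the protocol's expansion table, and literal application of the symptom condition.

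**What to change.** 1. Mark bleed/medication review at Weeks 2, 3 and 4 for both cohorts in protocol Appendix 1 and SAP Appendix 2, so that the schedule agrees with SAP 2.2.1. At those visits, have the patient complete any missing days on the device while the entry window is open.
2. State in SAP 2.3.2.4 that a bleed of type joint added by data change request without symptoms is counted as a joint bleed, and add a sensitivity analysis that excludes such bleeds. Protocol 4.5.8 carries the same symptom requirement, so it should be aligned or the departure recorded. This rule also covers the later 4-week intervals, which the added reviews do not reach.

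The cost is a few minutes of site time at visits already scheduled, or a telephone or portal review where mobile nursing replaces a site visit, plus one additional analysis. With ±2-day visits in the expansion cohort, a few days may still fall outside the window.
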